### 1.5. Potential of non-steroidal anti-inflammatory drugs as neuroprotective agents

Over the past decade, growing empirical evidence has suggested that common anti-inflammatory treatments may inhibit the pathogenesis of AD. Rheumatoid arthritis patients (and, later, leprosy patients treated with the anti-inflammatory drug dapsone) were shown to have a reduced occurrence of AD. Interest in possible inflammatory mechanisms in AD thus arose. There are now at least 21 reports that consider whether sustained use of anti-inflammatory treatments delays or prevents onset of AD . Several of these studies were population-based, and one used a prospective design. Two were conducted using cases and controls who were genetically matched (twins or siblings). These latter studies were designed to investigate whether a reduced risk, if any, associated with NSAID use resulted specifically from a delay in the symptomatic expression of a process that was otherwise genetically determined. Despite their variety in methodological approach, these studies have mostly converged in suggesting an inverse relationship between sustained prior use of anti-inflammatory compounds (especially NSAIDs) and risk of AD. The strength of the findings overall is suggested in a meta-analysis.

The above studies that report use of particular NSAIDs note that ibuprofen (the most commonly used NSAID) is also the most frequently reported drug among those with NSAID exposure, while naproxen is second in frequency. Among other notable points, those reports that mention dose and duration of exposure suggest that odds ratios (ORs) of about 0.5 do not require extended periods of exposure (although many exposed subjects surely have this) or large doses of NSAIDs.

The most recently published observations on the neuroprotective prospective of NSAIDs come from the Cache County Study, which enrolled over 5,000 (90%) of the county's eligible elderly population. The study's baseline cognitive screening interview included an extensive questionnaire covering prospective AD risk or protective factors, with emphasis on medical and pharmacologic exposures, and a medicine chest inventory of all drugs in current use. The study then examined the association of NSAID use and prevalent AD, adjusting for age, sex, education, and number of APOE

ε4 alleles. Odds ratios were examined simultaneously for other medication groups including aspirin and non-aspirin pain relievers (mainly acetaminophen), as well as H2 receptor antagonists and other treatments for dyspepsia and acid-peptic disease. The following odds ratio estimates (with 95% confidence intervals) and p-values were obtained:

| NSAIDs (no ASA, no H2Bs)      | OR = $0.43 (0.23 - 0.75)$ , p = $0.002$  |
|-------------------------------|--|
| Aspirin (no NSAIDs, no H2Bs)  | OR = $0.50 (0.34 - 0.73)$ , p = $0.0003$ |
| NSAIDs+ASA (no H2Bs)          | OR = $0.17 (0.04 - 0.48)$ , p = $0.0002$ |
| ≥ 2 NSAIDs (no H2Bs)          | OR = $0.14 (0.02 - 0.45)$ , p = $0.0002$ |
| APAP, etc. (no NSAIDs or ASA) | OR = $0.81 (0.55 - 1.18), p = 0.287$     |

where ASA is aspirin (typically used in low dose for cardiovascular prophylaxis), "APAP, etc." is non-ASA, non-NSAID analgesics (mostly acetaminophen), and H2Bs are histamine H2 receptor antagonists. One interpretation of these findings is that sustained low or moderate (not "anti-inflammatory") doses of cyclooxygenase inhibitors can produce the apparent prevention effect.

All of the above observational data suffer from several potential difficulties that may produce misleading results. The most obvious of these is difficulty in accurate classification of exposures. Demented subjects cannot provide their own pharmacologic history information, and reliance on current medicine usage (from a medicine chest review) is likely to be a poor indicator of sustained long-term use prior to onset of illness. This problem is likely to create substantial "noise" in the data, the usual result of which will be to mask or weaken the appearance of a relationship of AD to prior drug use, if one exists. Other difficulties may produce biased or spurious results. Those with AD may be less likely to demand or comply with prescriptions for anti-inflammatory treatments. Physicians may be less likely to prescribe these treatments when their patients are frail or demented. Other, unsuspected sources of confounding may also lead to spurious findings. For these reasons, observational data can only be regarded as preliminary or suggestive. Proof of any protective or beneficial effect with NSAIDs (or other drugs) must derive from clinical trials.

### 1.6. Rationale for study treatments and doses

The non-aspirin NSAIDs were first introduced in the 1960s as safer and more potent alternatives to high dose aspirin treatment for arthritis and other inflammatory conditions. Subsequent research showed that their anti-inflammatory activity is due to the inhibition of prostaglandin synthesis. In the late 1980s it was discovered that there are two prostaglandin synthetase enzymes, which were termed cyclooxygenase-1 (COX-1) and cyclooxygenase-2 (COX-2). COX-1 is an important constitutive enzyme that is essential for a number of biological activities, such as the protection of the stomach lining from the tissue-destructive effects of gastric secretions. By contrast, COX-2 is usually produced in response to pro-inflammatory stimuli. All non-aspirin NSAIDs marketed prior to 1999 are inhibitors of both COX-1 and COX-2. Two NSAIDs, celecoxib and rofecoxib, which were approved by the U.S. Food and Drug Administration (FDA) in 1999 for treatment of arthritis and

inflammation, are COX-2-selective compounds. In the doses commonly used for anti-arthritic effects, the selective inhibitors cause fewer adverse events (in particular, fewer gastric and duodenal ulcerations and bleeds).

In designing the Alzheimer's Disease Anti-inflammatory Prevention Trial (ADAPT), the investigators considered it important to test both a non-selective COX inhibitor and a selective COX-2 inhibitor. The safety of the selective COX-2 inhibitors makes them attractive for a primary prevention trial. However, none of the preliminary, observational data on the relationship of NSAID use and AD includes exposure to these compounds. Furthermore, both COX-1 and COX-2 have been observed repeatedly in brain. Because there is no current consensus on the function of either, nor on their possible relationship to AD pathogenesis, it is not known whether inhibition of COX-1, COX-2, or both is necessary for the postulated protective action of NSAIDs. In addition, although the safety advantage of the selective compounds has been demonstrated at relatively high, anti-arthritic doses, it is not clear that the same advantage will obtain at lower doses, such as those commonly reported in the observational evidence on NSAIDs and AD. Finally, if effective and well tolerated, the low-cost, over-the-counter (dual-inhibitor) NSAIDs could allow for a more cost-effective public health intervention.

Naproxen sodium was chosen as the conventional NSAID because:

- Naproxen is a frequently reported exposure in observational studies on NSAIDs and risk of AD, although less commonly reported than ibuprofen. The limited data available do not suggest an advantage of one drug over the other, either for safety or for their neuroprotective potential.
- Naproxen is a relatively strong inhibitor of COX-1 and a moderate COX-2 inhibitor. It should thus be a good compound to compare with a selective COX-2 inhibitor.
- Like the COX-2 inhibitors (but unlike ibuprofen), naproxen has a relatively long half-life of about 12 hours and should therefore maintain good plasma and cerebrospinal fluid levels when given in a b.i.d. regimen. Also, compared to pharmacologically equivalent over-the-counter formulations of ibuprofen, naproxen requires administration of fewer pills.

Celecoxib was chosen as the selective COX-2 inhibitor for the following reasons:

- It was the first selective COX-2 inhibitor approved by the FDA, and it remains the agent with the most post-marketing safety surveillance data.
- The safety data suggest that celecoxib has a side effect profile that is at least as favorable as rofecoxib, and it may produce less difficulty with fluid retention as a result of inhibition of COX-2 in the distal renal tubule.

The dose of naproxen sodium to be used in the trial is 220 mg b.i.d., because this dose has significant safety advantages over larger doses. Also, this dose is thought to be in the equivalent

range of NSAID use that has appeared in epidemiological studies to be potentially neuroprotective. In the Baltimore Longitudinal Study of Aging, the median reported daily dose of ibuprofen (the most common NSAID exposure) was about 800 mg/day. The approximate equivalent dose of naproxen sodium is 440 mg/day.

The trial's specified dose of celecoxib is 200 mg b.i.d., which appears to come close to achieving the full anti-inflammatory potential of this compound in humans while still maintaining a good safety profile. In clinical trials of celecoxib for treatment of rheumatoid arthritis, the 400 mg daily dose of celecoxib provided nearly the same efficacy as the 800 mg daily dose and little difference in safety from the 200 mg daily dose.

It is recognized that the doses of the trial's two treatments are not pharmacologically equivalent (the celecoxib dose being somewhat stronger). The chosen doses allow for the potential of maximum effect while maintaining reasonable safety. In addition, if one or both treatments prove efficacious, the combination of treatments and doses allows inferences regarding how the prevention is achieved. That is, we may be able to determine whether COX-1 inhibition is necessary for prevention of AD and whether full anti-inflammatory or lower doses contribute to the treatment effect.

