### **ADAPT Protocol**

### 2. Objectives

### **Primary objective**

• To evaluate the efficacy of naproxen sodium as compared to placebo, and of celecoxib as compared to placebo, for the prevention of AD

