# 8. Analysis plan

### 8.1. General principles

General principles for analysis include the following:

- The primary analysis will be performed according to participants' original treatment assignment (intention to treat), regardless of administered treatment
- All participants, including those who are found to be ineligible after randomization or those who withdraw from the study, will be counted in their assigned treatment group once that treatment assignment has been revealed
- All events following randomization will be counted
- Subjects with missing measures at a particular time will be excluded from analyses that
  require those measures but will not be excluded from other analyses for which data are
  available

Analyses will be done to look for differences in outcome between each of the groups receiving active treatment and the placebo-treated group. Results of analyses will be presented unadjusted and adjusted. Covariates to be used for adjusting treatment group effects will include field site (also a stratification variable), age at entry (a stratification variable in the form of age categories), APOE genotype, gender, and other prospective baseline risk factors chosen with clinical judgment and/or variable selection procedures such as forward selection. Exploratory analyses will be performed in which post randomization data, such as adherence to the assigned treatment regimen or treatment received, will be taken into account. In addition, treatment effects will be examined across various subgroups.

Formal adjustment procedures will not be used for p-values resulting from the comparisons of each of the active treatment groups with the placebo group or from multiple comparisons made during interim monitoring. In the comparisons of the active treatments to placebo, the two treatment comparisons (naproxen sodium vs. placebo and celecoxib vs. placebo) are viewed as tests of separate experimental hypotheses. With respect to interim monitoring, it is to be expected that numerous comparisons of treatment efficacy and safety must be performed over the course of a clinical trial. Rather than to adjust p-values for multiple comparisons, p-values will be interpreted as descriptive statistics of the evidence, and not as absolute indicators for a positive or negative result.

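### Section 1.6 hopes to learn about COX-1 and dose from two active arms in which selectivity and dose strength change together, and no naproxen-versus-celecoxib efficacy contrast is planned to support that

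*Protocol*

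**What the plan says.** Protocol section 1.6 describes the two active arms in terms that differ on two axes. On selectivity, "Naproxen is a relatively strong inhibitor of COX-1 and a moderate COX-2 inhibitor", while celecoxib is the COX-2-selective agent. On strength, naproxen is given at a dose chosen for its safety advantage over larger ones, and celecoxib at a dose "which appears to come close to achieving the full anti-inflammatory potential of this compound in humans". The section acknowledges the imbalance: "doses of the trial's two treatments are not pharmacologically equivalent (the celecoxib dose being somewhat stronger". Section 4.1 lists one dose level per drug.

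Section 1.6 then says that "if one or both treatments prove efficacious, the combination of treatments and doses allows inferences regarding how the prevention is achieved", and explains that "we may be able to determine whether COX-1 inhibition is necessary for prevention of AD and whether full anti-inflammatory or lower doses contribute". It also gives, as one reason for choosing naproxen, its suitability for comparison with a selective agent.

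The efficacy comparisons are narrower. The primary objective (section 2, repeated in Appendix B) is "To evaluate the efficacy of naproxen sodium as compared to placebo, and of celecoxib as compared to placebo". Section 8.1 says: "Analyses will be done to look for differences in outcome between each of the groups receiving active treatment and the placebo-treated group". It treats the two placebo comparisons as separate hypotheses without adjustment. The two drugs are set against each other only in the secondary objective on safety.

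**The concern.** Section 1.6 raises two explanatory questions, and the design and planned comparisons answer them only in part.

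First, selectivity and strength move together. No arm has the selective drug at a weaker dose or the non-selective drug at a fuller one. When the two drugs differ, the difference has two candidate causes and nothing in the trial to tell them apart.

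Second, a conclusion that COX-1 inhibition is needed depends on naproxen working and celecoxib not. That is a statement about the difference between the drugs. The protocol plans no estimate of that difference for Alzheimer's disease (AD), so the statement would have to come from one placebo test succeeding and the other failing. That pattern is common by chance when the drugs are equally good.

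What is at stake is the explanation given to the results. The two primary efficacy tests are not in question.

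**Working it through.** **1. The plan's own figure.** The calculation below uses the stated 80% power, so that comes first. Section 3.2 gives a 30% reduction, two-sided α = 0.05, 80% power and N = 2,625. The 1:1:1.5 ratio gives 750, 750 and 1,125. For one active-versus-placebo pair the active share is 750/1,875 = 0.4.

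- Events needed (Schoenfeld): (1.960 + 0.842)² / [0.4 × 0.6 × (ln 0.70)²] = 7.849 / 0.03053 = 257.1, so 258.
- Events expected over 7 years, from the section 3.2 incidence, mortality and 5% yearly loss, give cumulative AD risks of 0.1090 (active) and 0.1511 (placebo): 750 × 0.1090 + 1,125 × 0.1511 = 251.7.
- Power is about 79%, and N for 80% is 2,625 × 258/251.7 ≈ 2,690, within 3% of the stated figure.

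This agreement needs the 30% to be the net intention-to-treat reduction. If the section 3.2 drop-out and drop-in rates dilute a 30% on-treatment effect, power per comparison is about 41%.

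**2. What each result pattern can support.**

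| Result against placebo | Supported | Not supported |
|---|---|---|
| Celecoxib works | COX-1 inhibition is not necessary | – |
| Naproxen works | A full anti-inflammatory dose is not necessary | – |
| Only celecoxib works | First row | Whether dose or selectivity explains the difference |
| Both work, sizes differ | First two rows | Whether dose or selectivity explains the difference |
| Only naproxen works | Second row; greater dose strength does not readily explain it | That COX-1 inhibition is needed, without a direct contrast |

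**3. How often equal drugs look unequal.** The two test statistics share the placebo group, so their correlation is

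ρ = (1/1,125) / (1/1,125 + 1/750) = 0.40.

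At 80% power each statistic has mean 1.960 + 0.842 = 2.80. From the bivariate normal distribution, P(both significant) = 0.676. Then

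- P(exactly one) = 2 × (0.80 − 0.676) = 0.248, about 25%;
- P(naproxen only) = P(celecoxib only) = 0.80 − 0.676 = 0.124, about 12% each.

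Sensitivity, under an assumed power of 42% (close to the diluted reading in step 1): P(both) = 0.240 and P(exactly one) = 2 × (0.42 − 0.240) = 0.36, or 18% in each direction.

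**4. What a direct contrast would give.** With 750 against 750, the approximate 95% limits for the hazard ratio are the estimate multiplied and divided by exp(1.96 × 2/√D), where D is the number of AD events in the two arms.

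- D = 200: exp(0.277) = 1.32.
- D = 175: exp(0.296) = 1.34.
- If both drugs truly give 0.70, D is lower, 2 × 750 × 0.1090 ≈ 164, and the factor is 1.36.

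Power at two-sided 0.05, for assumed net hazard ratios against placebo (the protocol gives none for this contrast):

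| Better drug vs other drug | Events | Power |
|---|---|---|
| 0.70 vs 1.00 | 195 | 70% |
| 0.70 vs 0.90 | 185 | 40% |
| 0.70 vs 0.85 | 180 | 25% |
| 0.70 vs 0.80 | 174 | 14% |

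With the listed non-adherence diluting the effects, the powers are 44%, 23%, 15% and 9%.

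**The case against.** The strongest reply is that section 1.6 is careful. It admits that the doses are not equivalent, makes its statement conditional on efficacy, and says only that the investigators may be able to learn something. No mechanistic aim appears among the objectives. Section 8.1 treats p-values as descriptive, and nothing in the protocol says that a conclusion will be drawn by matching one p-value against the other. All of this stands, and it keeps the point small. It does not remove the confounding, and descriptive p-values are no substitute for an estimate of the difference.

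A reader might go further and infer that the dose question can never be answered, or that no result can separate dose from selectivity. The documents do not support either reading. A naproxen benefit at the weaker dose would itself indicate that full anti-inflammatory dosing is unnecessary, by the same logic that lets a celecoxib benefit speak on COX-1. A naproxen-only result also runs against a dose-strength explanation. The dose clause should therefore be narrowed and not deleted.

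A reader might also take the whole 25% as misleading. In that scenario both drugs work, so in the celecoxib-only half the conclusion that COX-1 inhibition is unnecessary is correct. A false claim that COX-1 inhibition is needed arises only in the naproxen-only half.

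Finally, an exploratory head-to-head hazard ratio is ordinary content for a statistical analysis plan, and that document is not at hand. Its absence from the protocol alone would be no finding. The point is that the protocol offers the inference itself while its own objectives confine between-drug comparison to safety.

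**Conclusion.** The point holds in limited form. A celecoxib-only benefit or a difference in effect size cannot be assigned to selectivity rather than dose, because the two vary together across the only active arms. A naproxen-only pattern has no planned efficacy contrast behind it. With equal true effects, 80% power per comparison and the planned allocation, about 12% of trials would show that pattern and falsely suggest that COX-1 inhibition is needed. The figure is about 18% under the assumed 42% power.

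These figures rest on a normal approximation and on the protocol's own event-rate assumptions. The result depends on the true effects being equal, which is the case that matters for a false signal. Severity is minor: this is one tentative statement in the rationale, and the sample size, randomization, endpoints and primary placebo comparisons are unaffected.

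**What to change.** **Section 1.6.** Keep the two inferences that the placebo comparisons support: a celecoxib benefit indicates that COX-1 inhibition is not necessary, and a naproxen benefit indicates that a full anti-inflammatory dose is not necessary. Add that a difference between the drugs cannot be split between selectivity and dose.

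**Sections 8.1 and 8.2.** Add the naproxen-versus-celecoxib hazard ratio for AD with its 95% confidence interval, from the same survival model. Label it exploratory and imprecise, with limits of roughly a factor of 1.32 to 1.34 either way on an estimated 175 to 200 events. State that any between-drug statement rests on this estimate and not on one placebo comparison being significant and the other not. If the statistical analysis plan already contains this contrast, a cross-reference is enough.

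**Cost.** A few sentences and one more contrast from the three-arm model. The price is a more modest mechanistic claim and a wide interval that will often be inconclusive. No change of dose, sample size or primary test is implied.

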### **ADAPT Protocol**

### 2. Objectives

### **Primary objective**

• To evaluate the efficacy of naproxen sodium as compared to placebo, and of celecoxib as compared to placebo, for the prevention of AD

### **Secondary objectives**

- To determine whether the study treatments can attenuate cognitive decline with aging
- To compare the safety of the study treatments with placebo, and with each other, regarding mortality and the occurrence of side effects

### 3. Design

### 3.1. Design features

The study is a randomized, multicenter clinical trial with three parallel treatment groups. Treatment assignment is stratified by field site and age category and employs a 1:1:1.5 assignment ratio among the three treatment groups. Treatment assignment is masked to participants and all field site personnel, including clinicians, neuropsychologists and psychometricians.

### 3.2. Sample size and power

Sample size is calculated to allow detection of at least a 30% reduction in the incidence of AD. Such a reduction will be detectable with 80% power and a two-sided  $\alpha = 0.05$  over 7 years of followup. Calculations were based on the log-rank statistic, under the following additional parameter assumptions:

- **Incidence rate**: It is estimated that the incidence rate of this population, "enriched" for family history of Alzheimer-like dementia, will be 2.5% in the first year, and that there will be a 10% proportional increase in each of the subsequent years (2.75% in the second year, 3.03% in the third year, and so on).
- Mortality rate: The mortality rates projected for the study population represent a base mortality rate in the first year of 4%, increasing by a factor of 8.5% in the subsequent years (4.34% in the second year, 4.71% in the third year, and so on).
- Losses to followup or refusals of further follow-up: A loss of 5% of participants each year is assumed for reasons such as participant relocation or refusal to continue in the study.
- Adherence to assigned treatment: The power of the study is affected 1) when participants assigned to active treatment stop taking the study medication and do not thereafter take an NSAID on a regular basis and 2) when participants assigned to placebo become regular NSAID users. The first situation is projected to occur in 15% of participants assigned to active medication during the first year and in an additional 5% for each of the remaining years. The second scenario is thought to be less probable (participants will be more likely to become intermittent, rather than regular, users of NSAIDs). It is therefore estimated that 2.5% of participants assigned to placebo will become regular NSAID users in each year.

Under the assumptions outlined above, the required sample size is approximately 2,625.

2. Objectives

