### **Executive summary**

An intervention that delays onset of Alzheimer's disease (AD) by several years would yield huge public health benefits. Several studies suggest that non-steroidal anti-inflammatory drugs (NSAIDs) may produce such a delay. NSAIDs may also attenuate progressive age-related cognitive decline (ARCD) when this condition represents a prodrome of AD. Both outcomes can be evaluated definitively only in randomized trials. Such trials can also examine attendant risks of long-term NSAID use in the moderate doses that appear to afford protection against AD and ARCD. Improved safety may be available with selective cyclooxygenase-2 (COX-2) inhibitors, but, owing to the newness of these compounds and the lack of relevant data, it is not known whether COX-2 inhibition offers the protective effect apparent with conventional NSAIDs.

The Alzheimer's Disease Anti-inflammatory Prevention Trial is a randomized, placebo-controlled, multicenter trial designed to test the efficacy of a non-selective NSAID and a selective COX-2 inhibitor for the prevention of AD and attenuation of ARCD. The treatment regimens, which are tested in parallel, are: naproxen sodium (220 mg b.i.d.), celecoxib (200 mg b.i.d.), and placebo. The trial is designed to enroll 2,625 dementia-free participants who are age 70 or older and have a history of Alzheimer-like dementia in a first degree relative. Participants will be evaluated with structured, standardized methods of assessment and diagnosis. Conspicuous decline in periodic cognitive assessment test results will identify participants with suspected incident dementia, who will then undergo further assessment.

The proposed sample size presumes 7 years of followup, with estimates of incidence beginning at 2.5% for the first year and increasing by a factor of 1.1 per year. It also takes into account attrition through mortality and other causes, and treatment "drop-outs" and "drop-ins." It should provide 80% power (2-tailed  $\alpha$ =0.05) to detect a 30% reduction in either active treatment group.

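### The 80% power stated for 2,625 participants does not follow from the protocol's own list of assumptions once drop-outs and drop-ins are counted

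*Protocol*

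**What the plan says.** Section 3.2 sets the target: "Sample size is calculated to allow detection of at least a 30% reduction in the incidence of AD". It continues: "Such a reduction will be detectable with 80% power and a two-sided" alpha of 0.05 over 7 years. The method is given as "Calculations were based on the log-rank statistic, under the following additional parameter assumptions", and the list that follows contains:

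- AD incidence of 2.5% in year 1, rising by a tenth each year;
- mortality of 4% in year 1, rising by 8.5% each year;
- loss to follow-up of 5% a year;
- drop-out in the active arms: "The first situation is projected to occur in 15% of participants assigned to active medication during the first year and in an additional 5" per cent for each later year;
- drop-in to regular NSAID use in the placebo arm of 2.5% a year.

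The section then concludes: "Under the assumptions outlined above, the required sample size is approximately 2,625".

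The Executive summary repeats the claim. It says that the size allows for attrition, drop-outs and drop-ins, and that the power is "to detect a 30% reduction in either active treatment group". Section 3.1 "employs a 1:1:1.5 assignment ratio among the three treatment groups", so each active-versus-placebo comparison has 750 against 1,125 participants.

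**The concern.** Drop-out that accumulates to 45% of the active arm and drop-in that accumulates to 17.5% of the placebo arm over seven years pull the two arms together under intention to treat. A sample size that allows for this must be well above one that does not. Yet 2,625 is close to what a plain log-rank calculation at a hazard ratio of 0.70 gives with no non-adherence at all.

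The claim at stake is the design claim for the primary objective. If 30% is what the drug does in people who take it, the chance of detecting it is well below the stated 80%, and a null result would be weaker evidence against a 30% effect than a reader of section 3.2 would believe.

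**Working it through.** **Inputs.** The rates, test, alpha and duration come from section 3.2, and the allocation from section 3.1. In each comparison the active share is 750/1,875 = 0.4, so p(1−p) = 0.24.

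**Step 1: reproduce the plan's figure without non-adherence.** Schoenfeld's formula for required events is D = (1.96 + 0.8416)² / [0.24 × (ln HR)²]. At HR 0.70, D = 7.849 / (0.24 × 0.1272) = 257.1, so 258. A life table with the stated incidence, mortality and loss gives 251–264 events in 1,875 participants, depending on whether deaths and losses are taken at mid-year or at year end.

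- Power with 251 events: Φ(√(251 × 0.24) × 0.3567 − 1.96) = Φ(0.81) = 79%. With 264 events: Φ(0.88) = 81%.
- Trial size for 80% power: 2,563 to 2,700. The stated 2,625 lies inside this range.
- A Markov log-rank calculation in fine time steps gives 76% for the same case. Simulation also gives 76%.

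**Step 2: add the stated non-adherence.** Section 3.2 gives the rates at which people drop out or in, but not the hazard they then have. The usual convention is assumed here: a drop-out returns at once to the placebo hazard, and a drop-in takes the full 0.70 hazard. At mid-year, with a fraction a of the active arm off drug and a fraction b of the placebo arm on an NSAID, the ratio of arm hazards is [1 − 0.3(1 − a)] / [1 − 0.3b].

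| Year | a | b | Ratio |
|---|---|---|---|
| 1 | 0.075 | 0.0125 | 0.725 |
| 2 | 0.175 | 0.0375 | 0.761 |
| 3 | 0.225 | 0.0625 | 0.782 |
| 4 | 0.275 | 0.0875 | 0.804 |
| 5 | 0.325 | 0.1125 | 0.825 |
| 6 | 0.375 | 0.1375 | 0.847 |
| 7 | 0.425 | 0.1625 | 0.870 |

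The average is about 0.80. Schoenfeld's formula then needs about 640 events, and about 256 are expected. Power is Φ(√(256 × 0.24) × 0.226 − 1.96) = Φ(−0.19) = about 42%.

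**Step 3: the full log-rank calculation.** The Markov version computes the log-rank numerator and variance step by step, and power is Φ(z − 1.96).

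- Percentages read as shares of those assigned: about 166 placebo and 90 active events, z = 1.74, power 41%.
- Percentages read as annual rates among those still adherent: z = 1.82, power 44%.
- Simulated log-rank tests (2,000 runs each) give 41% and 44%.

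At the stated rates, 80% power would take about 6,250 to 6,830 participants in total.

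**Step 4: vary what the protocol leaves open.** All results are two-sided with the stated cumulative non-adherence.

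| Variant | Power |
|---|---|
| Drop-outs keep half the benefit, drop-ins gain all of it | 55–57% |
| Drop-outs keep half, drop-ins gain half | 59–61% |
| Drop-outs keep three quarters, drop-ins gain nothing | about 70% |
| Immediate full switch, but no deaths and no losses | 50–55% |
| Immediate full switch, both active arms pooled against placebo | 56–60% |

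None reaches 80%.

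**Step 5: what 2,625 can detect.** Under the immediate switch, 80% power needs an on-treatment reduction of about 45–47%, which corresponds to an intention-to-treat hazard ratio of about 0.69.

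**The case against.** The strongest defence is that 30% is the net reduction between randomised groups. The Executive summary speaks of a reduction in a treatment group, and section 8.1 makes the primary analysis intention to treat. On that reading non-adherence could have been used to get from an on-drug effect of about 45% to a net 30%, and section 1.5 cites observational odds ratios of about 0.5, so such an on-drug effect was not out of view. The stated 80% would then be roughly right. This is a possible meaning, but the protocol does not state it. Section 3.2 lists drop-out and drop-in among the parameter assumptions of the power calculation, says that they affect power, and gives no other effect size. A reader might infer that the 80% is simply false. The text supports less than that: it does not say which 30% is meant, and the figure is wrong if it is the on-treatment effect.

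A second objection also stands in part. The figure of 41–44% rests on a hazard switch that section 3.2 does not specify. A reader might infer that each comparison is more likely to miss a true 30% on-treatment effect than to find it. That holds under the immediate full switch but not in the milder variants above, where power passes one half. The shortfall against 80% remains in all of them.

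Reading the yearly drop-out as non-cumulative gives 71–73% two-sided, and it conflicts with the wording that each later year adds a further 5%.

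Two further inferences should not be drawn. Section 9 only allows conditional-power methods and does not tie them to the section 3.2 effect, so the documents do not show that monitoring would be misdirected. Section 8.1 treats p-values as descriptive, which softens the risk of over-reading a null result but does not correct the stated power. The difference between 7 years of follow-up and the up-to-7-years entry in Appendix B is minor here: an assumed 2-year accrual inside the 7 years gives 40–42%.

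**Conclusion.** The point holds. With the assumptions that section 3.2 and the Executive summary say are included, 2,625 participants do not give 80% power for a 30% on-treatment reduction. Power per comparison is about 41–44% under an immediate full hazard switch, and about 55–70% if drop-outs keep half to three quarters of the benefit. The stated size matches, within about 3%, a calculation with non-adherence left out (required N 2,563–2,700).

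The conclusion rests on reading 30% as the on-treatment effect, on cumulative non-adherence as worded, and on a two-sided log-rank test in each 750-versus-1,125 comparison. The exact power depends on the unstated post-switch hazards. If 30% was meant as the net effect, the power figure is roughly right and the text that defines the effect is what needs repair.

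**What to change.** Keep N = 2,625 and amend section 3.2 and the Executive summary to say whether 30% is the on-treatment or the net intention-to-treat reduction.

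- **If on-treatment:** restate power per comparison as about 41–44%, give the assumed hazards after drop-out and drop-in, and show the range under milder assumptions. Add that 80% power requires an on-treatment reduction of about 45–47% (intention-to-treat hazard ratio about 0.69).
- **If net:** keep a power of roughly 76–80% and name the method, since the Markov log-rank and Schoenfeld results differ. Say that the 30% is what remains after drop-outs and drop-ins, and give the on-treatment reduction that this implies, about 45–47%. The statement that non-adherence was considered can then stay, because it describes the step from one effect to the other.

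The change is to wording only. It adds no participants or procedures. Its cost is a less favourable stated figure: either a lower power or a larger on-treatment effect than the present text suggests.
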